1.4.5 Nivolumab flat dose regimen

The safety and efficacy of 240 mg (monotherapy) Q2W flat dose of nivolumab has recently received FDA approval and is expected to be similar to 3 mg/kg Q2W dosing regimen. Using the PPK model, exposure of nivolumab at 240 mg flat dose is identical to a dose of 3 mg/kg for subjects weighing 80 kg, which is the approximate median body weight in nivolumab clinical trials. Across the various tumor types in the clinical program, nivolumab has been shown to be safe and well tolerated up to a dose level of 10 mg/kg, and the relationship between nivolumab exposure produced by 3 mg/kg and efficacy and safety has been found to be relatively flat. Given the similarity of nivolumab PK across tumor types and the similar exposures predicted following administration of 240 mg flat dose compared to 3 mg/kg, it is expected that the safety and efficacy profile of 240 mg nivolumab will be similar to that of 3 mg/kg nivolumab.

In addition, nivolumab 480 mg administered once every 4 weeks (Q4W) is currently under investigation. The less frequent dosing regimen is designed to

NU Study Number: NU 16L04
Other Study Number: CA 209-801

afford more convenience to the target patient populations. The nivolumab dose of 480 mg Q4W was selected based on clinical data and modeling and simulation approaches using PPK and exposure-response analyses of data from studies in multiple tumor types (melanoma, NSCLC, and RCC) to provide an approximately equivalent dose of nivolumab 3 mg/kg Q2W. Exposures following nivolumab 480 mg Q4W regimen are predicted to be within the exposure ranges observed at doses up to 10 mg/kg Q2W used in the nivolumab clinical program, and are not considered to put participants at increased risk. Hence, the flat dose of 480mg nivolumab is under investigation , and will be administered in this study after 4 months at the 240mg dose.

1.5 Metformin

1.5.1 Clinical safety, Development and Efficacy

Metformin is a well-studied drug, utilized by a large number of adults with diabetes. The following are considered contraindications to the use of metformin: hypersensitivity to metformin or any component of the formulation; kidney dysfunction (serum creatinine ≥ 1.5 mg/dL in males or ≥ 1.4 mg/dL in females) or abnormal creatinine clearance from any cause (including shock, acute myocardial infarction, or septicemia); acute or chronic metabolic acidosis. In addition, it is generally recommended to temporarily discontinue metformin in patients undergoing radiologic studies in which intravascular iodinated contrast media are utilized. It is also recommended that metformin be used cautiously in patients with congestive heart failure requiring pharmacologic management, because the risk of lactic acidosis may be increased secondary to hypoperfusion.

Metformin was developed as an anti-diabetes drug. However, recent research have found interesting anti-tumor properites of metformin. Of note, the immune modulating properties leading to significant anti-tumor effect has not yet been explored in a clinical trial setting.

1.6 Exploratory Studies

Exploratory biomarker studies will be pursued involving tissue samples and peripheral blood. These studies will focus on the use of biomarkers to predict response to immunotherapy. Current body of evidence suggests that PD-L1 expression and TIL (tumor infiltrating lymphocyte) at tissue and peripheral blood lymphocyte phenotype markers may correlate with response to immunotherapy although still controversial. Tissue and blood samples will be stored to explore further molecular biomarkers including but not limited to genomic, immunologic or proteomic alterations.

2.0 OBJECTIVES & ENDPOINTS

2.1 Primary Objective & Endpoint

To assess anti-tumor activity of the combination treatment of metformin with nivolumab in patients with non-small cell lung cancer with and without prior exposure to PD-1/PD-L1 inhibitors: Anti-tumor activity will be assessed by objective response rate (ORR, complete response and partial response) using RECIST criteria v1.1.

2.2 Secondary Objectives & Endpoints

2.2.1 To assess the efficacy of the combination treatment of metformin with nivolumab according to depth, duration, and persistence of response, disease control rate (DCR; CR, PR, and SD at 24 weeks), progression-free survival (PFS), and overall survival (OS) in patients with non-small cell lung cancer with and without prior exposure to PD-1/PD-L1 inhibitors using RECIST criteria v1.1. Depth of response (SD or PR) is defined as the change in the sum of the largest tumor diameters per RECIST.

NU Study Number: NU 16L04
Other Study Number: CA 209-801

- 2.2.2** To assess the efficacy of the combination treatment of metformin with nivolumab according to depth, duration, and persistence of response, ORR, DCR, PFS, and OS in the above population using immune-related RECIST (irRECIST) criteria. Depth of response (SD or PR) is defined as the change in the sum of the largest tumor diameters per irRECIST.
- 2.2.3** To assess the safety and tolerability profile of the combination treatment of metformin with nivolumab in the above population using CTCAE version 4.03.

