6.4 Secondary Endpoints

6.4.1 To assess the efficacy of the combination treatment of metformin with nivolumab according to depth, duration, and persistence of response, disease control rate (DCR; CR, PR, and SD at 24 weeks), progression-free survival (PFS), and overall survival (OS) in patients with non-small cell lung cancer with and without prior exposure to PD-1/PD-L1 inhibitors using RECIST criteria. Depth of response (SD or PR) is defined as the change in the sum of the largest tumor diameters per RECIST criteria.

NU Study Number: NU 16L04
Other Study Number: CA 209-801

6.4.2 To assess the efficacy of the combination treatment of metformin with nivolumab according to depth, duration, and persistence of response, ORR, DCR, PFS, and OS in the above population using immune-related response criteria (irRC) criteria. Depth of response (SD or PR) is defined as the change in the sum of the largest tumor diameters per irRECIST.

6.4.3 To assess the safety and tolerability profile of the combination treatment of nivolumab and metformin in the above population using CTCAE version 4.03

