10.2 Sample Size and Accrual

Up to 49 patients (Arm A=24, Arm B=25) will be entered into the trial based on optimal Simon two stage design as below.

Arm A: In the first stage, 9 patients will be entered. If no patients show a response, then the trial will be terminated due to inactivity of the treatment. If 1 or more of 9 show a response, then an additional 15 patients will be added. If 2 or fewer of 24 show a response, then the trial will conclude that the response rate could be as low as 5%. If 3 or more respond, then the trial will conclude that the response rate is at least 20%. This design has a 20% chance of falsely concluding the rate is 5% (false negative Type II error rate = 20%, or power = 80%), and a 10% chance of falsely concluding that the rate is 20% (false positive Type I error rate = 10%). There is a 63% probability of early termination of the trial when the true response rate is 5%.

Arm B: In the first stage, 12 patients will be entered. If 2 or less patients show a response, then the trial will be terminated due to inactivity of the treatment. If 3 or more of 12 show a response, then an additional 13 patients will be added. If 7 or fewer of 25 show a response, then the trial will conclude that the response rate could be as low as 20%. If 8 or more respond, then the trial will conclude that the response rate is at least 40%. This design has a 20% chance of falsely concluding the rate is 20% (false negative Type II error rate = 20%, or power = 80%), and a 10% chance of falsely concluding that the rate is 40% (false positive Type I error rate = 10%). There is a 56% probability of early termination of the trial when the true response rate is 5%.

Due to inevaluable patients and dropout, target accrual will be 51 patients. It is anticipated that 2 patients will be accrued per month so that accrual to this study will take 2 years.

Thus, this study will be a single institution trial with duration of enrollment being 2 years. The study will be done via both internal and external referral system. Being one of the busiest lung cancer programs in the area with good advertisement plan towards partnering institutions on this clinical trial, the above accrual plan is deemed to be a feasible one.

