10.3 Data Analyses Plans

Summary of Analytic plan for primary objective	Summary of Analytic plan for secondary objectives

Please refer to the below sample size justification for the parallel Simon's two stage design which defines how the endpoints are met.
 
For Group A. Estimated ORR for historical control is 20% versus target ORR of 40% for nivolumab and metformin combination treatment.
	
Depth of response: waterfall plot Duration and persistence of response: swimmer's plot PFS: PFS at 1 and 2 years (Kaplan-Meier analysis) OS: OS at 1 and 2 years (Kaplan-Meier analysis) ORR, DCR by irRC (descriptive statistics,

NU Study Number: NU 16L04
Other Study Number: CA 209-801

For Group B. Estimated ORR for refractory patients is 5% versus target ORR of 40% for niovulomab and metformin combination treatment.
	
exact binomial confidence intervals) We will use descriptive statistics and graphical displays to evaluate change in serum biomarkers between pre- and post-treatment. A Wilcoxon signed rank test will be used to determine if there is a statistically significant change in serum biomarkers. Toxicities will be tabulated by type and grade.

--	---

The primary analysis will be on the evaluable analysis set, including all evaluable patients regardless of drug exposure. Clinical benefit rate will be defined as stable disease (for ≥ 12 weeks), complete or partial response by both the Response Evaluation Criteria in Solid Tumors (RECIST) and irRECIST. Maximum response prior to disease progression will be used. The overall response rate will be estimated by the proportion of overall response, and its 80% confidence interval (CI) and 95% CI will be estimated using the exact binomial distribution.

Additionally, we will evaluate overall response rate, defined as complete or partial response using RECIST guidelines in a similar manner. We will also perform similar analyses using Immune Related RECIST (irRECIST). Duration of response, defined as the duration from the first documentation of clinical benefit to the first documented progressive disease or death of any cause, whichever occurs first, will also be analyzed. For patients alive and progression-free at the time of data cut off, duration of response will be censored as of the last tumor assessment date. Duration of response will only be evaluated for the subgroup of patients with a clinical benefit using the Kaplan-Meier method.

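### Depth of response is defined only for patients with SD or PR, so a waterfall plot that follows the definition omits those whose best response is PD and any complete responders

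*Combined protocol and SAP*

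**What the plan says.** The definition appears four times, each time with SD or PR in brackets:

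- Section 2.2.1 (RECIST): "Depth of response (SD or PR) is defined as the change in the sum of the largest tumor diameters per RECIST".
- Section 2.2.2 (irRECIST): "Depth of response (SD or PR) is defined as the change in the sum of the largest tumor diameters per irRECIST".
- Section 6.4.1 (RECIST): "Depth of response (SD or PR) is defined as the change in the sum of the largest tumor diameters per RECIST criteria".
- Section 6.4.2 (irRECIST): the same sentence as in 2.2.2.

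The analysis table in section 10.3 has one line on it: "Depth of response: waterfall plot". It names no plot population, no rule for which change is plotted, and no handling of patients without a follow-up scan.

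Two other sentences in 10.3 come close but do not fill the gap. The analysis set is stated for a different analysis: "The primary analysis will be on the evaluable analysis set, including all evaluable patients regardless of drug exposure". The timing rule, "Maximum response prior to disease progression will be used", does not bring in a patient whose best response is PD.

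**The concern.** The definition selects patients on the outcome that the plot is meant to display. Whether a patient is SD, PR, PD or CR depends largely on the change in the target-lesion sum, so limiting the display to two of the four categories cuts off both ends of the distribution. In most advanced-disease settings the PD end is the more populated one, and removing it shifts the picture towards shrinkage.

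Each group is uncontrolled, so no concurrent arm carries the same selection and a reader has nothing to calibrate the plot against.

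Two features of this protocol add to the problem:

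- Section 4.4 allows treatment to continue after initial progression and foresees later regression of lesions. A patient whose best RECIST response is PD falls outside the RECIST definition even if the target lesions then shrink.
- Under section 6.2.1 a new lesion means PD by RECIST, whereas irRECIST adds new measurable lesions to the tumour burden. The same patient can be PD by one system and irSD or irPR by the other. The RECIST and irRECIST plots could then show different patients.

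**Working it through.** The plan states no figure for this endpoint, so there is none to reproduce. The check has three parts: the text, a count, and an illustration of direction.

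**1. Text.** The limit stands in all four definitions, across two sections, so a one-off slip is unlikely. Nothing in 10.3 restores PD or CR.

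**2. Count of missing bars.** The arm sizes come from section 10.2: "Up to 49 patients (Arm A=24, Arm B=25) will be entered into the trial". The share with PD as best response is not in the documents and is assumed.

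Missing bars = arm size × PD share, plus any CRs.

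| Patients | 20% PD | 30% PD | 50% PD | 60% PD |
|---|---|---|---|---|
| Arm A, 24 | 4.8 | 7.2 | 12.0 | 14.4 |
| Arm B, 25 | 5.0 | 7.5 | 12.5 | 15.0 |
| Both, 49 | 9.8 | 14.7 | 24.5 | 29.4 |

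At 30-50% this is about 7-12 patients per fully enrolled arm. An arm that stops at stage 1 has 9 or 12 patients, and the same shares give 2.7-4.5 or 3.6-6.0.

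**3. Direction.** Assumed mean changes are PD +20%, SD 0%, PR -50% and CR -100%. None comes from the documents.

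- *ORR 20% (all PR), SD 40%, PD 40%.* All patients: 0.20 × (-50) + 0.40 × 0 + 0.40 × 20 = -2.0%. SD and PR only: 0.20 × (-50) / 0.60 = -16.7%. The share of bars at PR level rises from 20% to 0.20/0.60 = 33%.
- *ORR 40% (all PR), SD 20%, PD 40%.* All patients: -20 + 8 = -12.0%. SD and PR only: -20/0.60 = -33.3%. PR-level bars rise from 40% to 67%.
- *ORR 20% with 5% CR and 15% PR, SD 40%, PD 40%.* All patients: -5 - 7.5 + 8 = -4.5%. SD and PR only: -7.5/0.55 = -13.6%. The gap is smaller because the CRs have gone too.
- *ORR 5%, all CR, SD 75%, PD 20%.* All patients: -5 + 4 = -1.0%. SD and PR only: 0.0%. Here the restricted plot looks worse.

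The last case shows when the sign turns. With no PRs, the restricted mean is 0, and the restricted plot looks better only if 20 × PD share exceeds 100 × CR share, that is, if PD is more than five times CR. Here 20% is less than 5 × 5% = 25%.

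A grid of 54 scenarios was run: ORR 5, 20 or 40%; PD 20, 40 or 60%; CR 0, 2 or 5%; PD change +20 or +30%. The restricted mean looked better in 53, and the case just shown was the one exception.

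**Growth bars.** If best change is plotted, no patient with SD or PR as best response can show a target-lesion rise that meets the PD rule in 6.1.7 (20% and 5 mm). This depends on plotting best change; the definition says only change and names no time point.

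**The case against.** The strongest reply is that the plan never limits the plot itself. Where it restricts an analysis it says so, as for duration: "Duration of response will only be evaluated for the subgroup of patients with a clinical benefit using the Kaplan-Meier method". Depth has no such sentence, a waterfall plot usually shows everyone with a measurement, and the bracket could be a loose gloss on the word response. This stands in part. A reader might infer that the plan expressly bars PD and CR from the figure; it does not, and the bias arises only if the plot follows the definition. But if the plot shows everyone, it departs from an endpoint written the same way four times, and one of the two must change.

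It can also be said that depth among patients with disease control is a legitimate conditional summary. That is true if it is labelled so, but the plan gives no such label.

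Other stronger readings are not supported:

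- *Every progressor is lost.* No. Only patients whose best response is PD drop out.
- *Both exclusions flatter the treatment.* No. Dropping CRs works the other way.
- *The selection spoils a comparison of the arms.* Section 1.3.2 gives the groups different questions, 10.2 gives them separate two-stage designs, and no between-arm comparison is planned. At most, different PD shares would put the two plots on different bases.

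**Conclusion.** The definition is wrong as written. Taken literally, it leaves out patients whose best response is PD and complete responders, and section 10.3 does not bring them back. On an assumed 30-50% PD, about 7-12 of 24-25 bars per fully enrolled arm would be missing. The remaining picture would be too favourable unless CRs are common relative to PD. The count rests on the assumed PD share and on both arms completing stage 2; the size of the shift rests on the assumed mean changes.

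The consequence is limited. Depth is descriptive, with no test or threshold attached. Patients with PD still count as non-responders in ORR, as failures in DCR and as events in PFS. The primary ORR decision, the sample size and the error rates are unaffected, so this is a minor point, though a clear one.

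**What to change.** In 2.2.1, 2.2.2, 6.4.1 and 6.4.2, delete the bracketed limit. Define depth of response as the best percentage change from baseline in the sum of target-lesion diameters (in tumour burden for irRECIST), whatever the response category, in all treated patients with a baseline and at least one post-baseline measurement.

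In 10.3:

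- state this as the waterfall population for each arm;
- mark the bars of patients with PD by new or non-target lesions;
- report the number of treated patients with no post-baseline scan.

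The cost is a wording change in five places. The scans and measurements are already collected, and no design figure moves.

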2.3 Exploratory Objectives & Endpoints

- 2.3.1** To assess the immune-related tumor and blood biomarkers including T cell markers and their association with treatment response in the above population
- 2.3.2** To assess the dynamic change in both immune and genomic biomarkers in blood that may correlate with response to metformin.

3.0 PATIENT ELIGIBILITY

The target population for this study is all patients with advanced non-small cell lung cancer with and without prior exposure to PD-1 or PD-L1 inhibitors. This trial will be conducted at Northwestern University with the potential of opening the trial at other institutions.

A total of 51 subjects will be needed for this trial. Approximately 4 potentially eligible patients are seen per month, and it is anticipated that at least 2 per month will be accrued. Potential patients may be referred to the Principal Investigator (PI) at Northwestern University, [name], at [contact] or [contact].

Eligibility will be evaluated by the study team according to the following criteria. Eligibility waivers are not permitted. Subjects must meet all of the inclusion and none of the exclusion criteria to be registered to the study. Study treatment may not begin until a subject is registered. Please refer to Section 11.3 for complete instructions regarding registration procedures.

3.1 Inclusion Criteria

- 3.1.1** Patients must have histologically confirmed, locally advanced or metastatic stage IV or non-resectable stage III non-small cell lung cancer (NSCLC).
- 3.1.2** Patients may have received any number and type of prior treatment regimens for their NSCLC (aside from patients in Arm A, who cannot have had PD-1/PD-L1 inhibitors).
- 3.1.3** Arm A: patients must be treatment naive to PD-1/PD-L1 inhibitors including but not limited to durvalumab, pembrolizumab, atezolizumab, nivolumab, and avelumab.

Arm B: patients' tumor must be either refractory to or progressed on one of the above agents.

NOTE: Prior treatment may include any number of PD-1/PD-L1 inhibitor therapies given as either a single-agent or in combination with chemotherapy..

NOTE: Patients must be eligible to receive the next line of therapy and not be suspected of having pseudoprogression. Both cases are defined by initial PD or PD after CR, PR, or SD using RECIST criteria, respectively.

NU Study Number: NU 16L04
Other Study Number: CA 209-801

3.1.4 Patients must have measurable disease according to the standard RECIST version 1.1.

NOTE: CT scans or MRIs used to assess the measurable disease must have been completed with 28 days prior to the study drug initiation.

3.1.5 Patients need to have adequate kidney, bone marrow, and liver functions ≤ 14 days of registration as specified below:

absolute neutrophil	$\geq 1,000/\text{mCL}^*$
platelets	$\geq 50,000/\text{mCL}^*$
hemoglobin	$\geq 8 \text{ g/dL}$
total bilirubin	≤ 1.5 times the institutional upper limit of normal (ULN) (or ≤ 3 times ULN in case of liver metastasis or Gilbert Syndrome)
AST(SGOT)/ALT(SPGT)	$\leq 2.5 \times$ institutional ULN (or ≤ 5 times ULN in case of liver metastasis)
creatinine	$\leq 1.4 \text{ ng/mL}$ for females; $\leq 1.5 \text{ ng/mL}$ for males** ng/ml

*Transfusion and/or growth factor are permitted within any timeframe.

**Patients with creatinine $\leq 2.0 \text{ ng/mL}$ may still be eligible if in the opinion of the investigator, the benefits of treatment outweigh the risks.

3.1.6 Patients must be age ≥ 18 years; both male and female are eligible.

3.1.7 Patients must exhibit an ECOG performance status of ≤ 2 .

3.1.8 Patients must have the ability to understand and the willingness to sign a written informed consent prior to registration on study.

3.1.9 Females of child-bearing potential (FOCBP) and men who are sexually active must agree to follow instructions for method(s) of contraception for the duration of treatment and the designated post-treatment period (see Appendix C for details on appropriate contraception methods)

NOTE: A FOCBP is any woman (regardless of sexual orientation, having undergone a tubal ligation, or remaining celibate by choice) who meets the following criteria:

- *Has not undergone a hysterectomy or bilateral oophorectomy*
- *Has had menses at any time in the preceding 12 consecutive months (and therefore has not been naturally postmenopausal for > 12 months)*

3.1.10 FOCBP must have a negative pregnancy test ≤ 7 days prior to registration on study.

3.1.11 Patients with known history of central nervous system (CNS) metastases are eligible if CNS disease has been radiographically and neurologically stable for at least 6 weeks prior to study registration and do not require corticosteroids (of any dose) for symptomatic management.

NOTE: CNS imaging is only required at baseline for patients with known history of CNS metastases.

3.1.12 Patients must have the ability to swallow oral medications.

NU Study Number: NU 16L04
Other Study Number: CA 209-801

3.1.13 Patients who are known to be EGFR- or ALK-positive must have received prior EGFR- or ALK-targeted therapy, respectively.

NOTE: In such cases, documentation of EGFR mutation or ALK translocation status should be provided if available.

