Group A and Group B will address two clinical questions. Group A is designed to assess possible synergistic effect of the combination treatment in immunotherapy naïve patients whereas group B is designed to determine whether the combination treatment of metformin with immunotherapy can overcome resistance to single agent PD-1/PD-L1 inhibitors.

Group A: In order to demonstrate synergy in anti-tumor effect, ORR of the combination treatment will be compared to that of historical control (20%) reported in phase 3 single agent nivolumab trials in lung cancer (CheckMate057 and CheckMate017). Optimal Simon's two stage design will be used with target ORR of 40% versus control ORR of 20% (type 1 error rate of 0.1 and power of 0.8)

Group B: In order to find signal in patients with prior exposure to single agent PD-1/PD-L1 inhibitors, ORR of the combination treatment will be described. Optimal Simon's two stage design will be used with target ORR of 20% versus control ORR of 5% (type 1 error rate of 0.1 and power of 0.8).

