1.4.2 Clinical efficacy

In a phase 1 (1, 3, and 10 mg/kg nivolumab doses) dose-escalation study the 3 mg/kg dose was chosen for expanded cohorts. Among 236 patients, objective responses (ORs) (complete or partial responses [CR or PR]) were seen in NSCLC, melanoma, and RCC. ORs were observed at all doses. Median OS was 16.8 months across doses and 20.3 months at the 3 mg/kg dose. Heavily pretreated patients with NSCLC treated with nivolumab (1, 3, or 10mg/kg) achieved median OS across all dose cohorts of 9.9 months with response rates of 17% and median duration of response 17 months ⁸. In addition, responses were similar between both squamous and non-squamous carcinoma cohorts in this study. A subsequent phase 3 study compared nivolumab to docetaxel in second-line treatment setting of advanced squamous cell carcinoma among 272 patients. Nivolumab arm demonstrated superior median OS (9 vs. 6 months), 1 year survival rate (42 vs. 24%), response rates (20 vs. 9%), and significantly lower rates of grade 3-4 treatment related adverse events (7 vs. 55%) ⁹. These results supported the FDA approval of nivolumab for second-line treatment of advanced squamous cell carcinoma following treatment with platinum-based chemotherapy.

Nivolumab also has clinically meaningful activity in RCC. A phase II study treated 168 patients with advanced clear cell RCC with progression after agents targeting VEGF pathway at three doses of nivolumab (0.3, 2 and 10mg/kg) ¹⁰. Median overall survival was 18, 25, and 24 months for the three dose cohorts, respectively. More recently 821 patients previously treated with anti-angiogenic therapy were randomized to either nivolumab (3mg/Kg every 2 weeks) or everolimus (10mg daily).¹¹ The median overall survival was 25.0 months (95% confidence interval [CI], 21.8 to not estimable) with nivolumab and 19.6 months (95% CI, 17.6 to 23.1) with everolimus. The hazard ratio for death with nivolumab versus everolimus was 0.73 (98.5% CI, 0.57 to 0.93; P=0.002), which met the prespecified criterion for superiority (P≤0.0148). Response rates were in average 20% with only 11% incidence of grade 3-4 treatment-related adverse events.

NU Study Number: NU 16L04
Other Study Number: CA 209-801

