1.4.3 Clinical Safety

For nivolumab monotherapy, the safety profile is similar across tumor types (investigator brochure v 2015). The only exception is pulmonary inflammation adverse events (AEs), which may be numerically greater in subjects with NSCLC, because in some cases, it can be difficult to distinguish between nivolumab-related and unrelated causes of pulmonary symptoms and radiographic changes. There is no pattern in the incidence, severity, or causality of AEs to nivolumab dose level. Safety data for subjects with previously treated advanced or metastatic NSCLC treated with nivolumab monotherapy in CA209017 (131 subjects), CA209057 (287 subjects), and CA209063 (117 subjects) were pooled and safety analyses were performed for these pooled subjects who receiving nivolumab monotherapy (a total of 535 subjects)(investigator brochure v 2015). Based on the pooled analyses, nivolumab monotherapy at a dose of 3 mg/kg administered IV Q2W has an acceptable safety profile, as demonstrated by the frequency, severity, and types of AEs, drug-related deaths, SAEs, and AEs leading to discontinuation. The most common adverse events were fatigue (19.6%), decreased appetite (12.3%), nausea (12.0%), and asthenia (10.5%). The majority of drug-related AEs were of Grade 1-2 in severity.

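### Arm A is tested against a 20% response rate from previously treated patients but sets no minimum number of prior regimens, so its stated error rates hold only if 20% is also the nivolumab-alone rate in the patients enrolled

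*Combined protocol and SAP*

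**What the plan says.** **The control.** Section 1.3.2 sets Group A against a "historical control (20%) reported in phase 3 single agent nivolumab trials in lung cancer", naming CheckMate 057 and 017, with the aim of showing synergy. Section 10.3 repeats the figures: "Estimated ORR for historical control is 20% versus target ORR of 40% for nivolumab and metformin combination treatment".

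**Where the 20% comes from.** Section 1.4.2 says of the squamous trial: "A subsequent phase 3 study compared nivolumab to docetaxel in second-line treatment setting of advanced squamous cell carcinoma among 272 patients". It reports a 20% response rate on nivolumab. Section 1.4.3 covers both trials, identified by their CA209 numbers: "Safety data for subjects with previously treated advanced or metastatic NSCLC treated with nivolumab monotherapy in CA209017 (131 subjects), CA209057 (287 subjects". So second-line is explicit for one trial, and previously treated is stated for both.

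**Who may enter Arm A.** Criterion 3.1.2: "Patients may have received any number and type of prior treatment regimens for their NSCLC", with PD-1/PD-L1 inhibitors as the only exception there for Arm A. Criterion 3.2.2 also bars other immunotherapies. Prior treatment is compulsory only for known EGFR- or ALK-positive disease (3.1.13). No minimum or maximum number of prior lines is given.

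**Analysis.** Sections 10.1 to 10.3 plan outcome by PD-L1 level and, in Arm B only, by type of prior checkpoint-inhibitor failure. They plan nothing by line of therapy.

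**The concern.** Arm A has no concurrent control. Responses beyond those expected from nivolumab can be attributed to metformin only if 20% is what nivolumab alone would achieve in the patients enrolled. The figure comes from previously treated patients, while eligibility lets in patients with no prior regimen and patients with many. If the enrolled mix would respond to nivolumab alone at a rate above 20%, the arm can pass with no contribution from metformin. If below, a real contribution can be missed. Either way the stated 10% type I error and 80% power do not describe the test. Section 1.3.1 says the result may lead to a pivotal phase 3 trial.

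**Working it through.** **Inputs**
- Control 20%, target 40%: 1.3.2 and 10.3, Group A. Type I error 0.10 and power 0.80: 1.3.2.
- Boundaries for 20% versus 40%: stop at 2 or fewer of 12, positive at 8 or more of 25. Section 10.2 and the Study Summary print these under Arm B. They are the plan's only boundaries for the pair of rates that 1.3.2 and 10.3 assign to Group A.
- 17% response rate in heavily pretreated NSCLC, over three nivolumab dose cohorts: 1.4.2.
- Share of untreated patients f and their nivolumab-alone response rate q: not in the documents, so assumed.

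**Formula.** For a true response rate p,

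P(pass) = Σ (x = 3 to 12) C(12,x) p^x (1−p)^(12−x) × P[Bin(13,p) ≥ max(0, 8−x)].

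**Step 1: reproduce the plan.** At p = 0.20 the chance of stopping at stage 1 is 0.0687 + 0.2062 + 0.2835 = 0.558, which matches the printed 56% (10.2 attaches that figure to a 5% rate). P(pass) is 0.099 at 20% and 0.815 at 40%. A search for the optimal Simon design for 20% versus 40% returns exactly these boundaries.

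**Step 2: no metformin effect, different nivolumab-alone rate**

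| Nivolumab-alone rate | P(pass) |
|---|---|
| 15% | 0.023 |
| 17% | 0.045 |
| 20% | 0.099 |
| 21.25% | 0.130 |
| 22.5% | 0.166 |
| 25% | 0.252 |
| 30% | 0.456 |

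A shift of five points, from 20% to 25%, multiplies the false-positive rate by about 2.5 (0.252/0.099).

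**Step 3: what mix gives those rates.** Take previously treated patients at 20% and the same mix in both stages, so p = 0.20(1−f) + qf. For example, f = 0.25 and q = 0.25 give 0.150 + 0.0625 = 0.2125.

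| Assumed q | f = 25%: p, P(pass) | f = 50%: p, P(pass) |
|---|---|---|
| 25% | 21.25%, 0.130 | 22.5%, 0.166 |
| 30% | 22.5%, 0.166 | 25%, 0.252 |
| 35% | 23.75%, 0.207 | 27.5%, 0.350 |
| 40% | 25%, 0.252 | 30%, 0.456 |

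**Step 4: the other direction.** If the arm resembled the heavily pretreated patients of 1.4.2 (17%), a true doubling to 34% would pass with probability 0.620. A true 20-point gain to 37% would pass with probability 0.728. The design gives 0.815 for 20% to 40%.

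**Step 5: the rule printed under Arm A.** Section 10.2 and the Study Summary give Arm A the 5% versus 20% design: stop at 0 of 9, positive at 3 or more of 24. Under that rule a 20% rate with no metformin effect already passes with probability 0.805, and 25% with probability 0.903. This label conflict is a separate defect, and it decides which error rates apply.

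**The case against.** **The inflation is assumed.** The documents give no untreated share and no untreated response rate, not even whether it lies above or below 20%. This stands. A reader might infer from the table that Arm A's true type I error is 25% or 46%, or that half the arm will be untreated. Nothing supports either reading: a 25% share at a 25% rate gives only 0.130. Nor do the documents support a nivolumab-alone rate below 17%. Starting from 15%, a doubling to 30% would pass with probability 0.456, but the lowest NSCLC figure the protocol reports is 17%.

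**Entry with no prior regimen is inferred.** Criterion 3.1.3 has a note that patients must be eligible for the next line of therapy, which could hint at prior treatment. But the note follows the Arm B text on progression and sets no minimum. The separate requirement in 3.1.13 would also be largely redundant if everyone needed a prior line.

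**Other mismatches.** A reader might add PD-L1 level, ECOG 0–2 and EGFR/ALK status to the list. The documents do not say what the control trials required on these, so only line of therapy can be argued.

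**This is proof of concept.** Imperfect historical comparability is a known limit of single-arm phase 2 trials, and section 3.0 deliberately targets all advanced NSCLC. That lowers the severity. It does not remove the gap, because the plan states error rates and a synergy aim without the condition they depend on.

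**Conclusion.** The mismatch is in the text, and nothing in the analysis plan addresses it. The 20% describes previously treated patients, Arm A does not require prior treatment, and results are not separated by line. The 10% and 80% for 20% versus 40% are conditional on a 20% nivolumab-alone rate in the enrolled mix. If that condition fails, the false-positive rate runs from 0.130 to 0.456 over the assumed mixes. At the protocol's own 17%, power to detect a doubling is 0.62. The direction and size of any actual bias cannot be established from the documents. The calculations also assume that the 20% versus 40% boundaries govern Arm A, as 1.3.2 and 10.3 imply and 10.2 contradicts. This should be fixed, but it does not invalidate the design.

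**What to change.** 1. Reconcile which boundaries apply to Arm A. Sections 1.3.2 and 10.3 give it 20% versus 40%, whereas 10.2 and the Study Summary print 5% versus 20% under that label.
2. State in 10.2 and 10.3, before further responses are reviewed, that the comparison with 20% and any synergy conclusion apply to Arm A patients with at least one prior systemic regimen for advanced disease. Date the change: the document is at Amendment 5, and the metformin supply switch in 8.2.9 suggests that treatment is under way.
3. Report Arm A response rates, with the exact confidence intervals already planned in 10.3, separately for patients with no prior regimen and with at least one.
4. If all Arm A patients stay in the two-stage count, state that the 10% and 80% are conditional on a 20% nivolumab-alone rate in the enrolled mix, and show the pass probability over a range of rates as in Step 2.

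A null weighted by the enrolled mix is not a workable substitute. It needs an untreated rate that the documents do not give, and the final mix is unknown when stage 1 is read.

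**Cost.** Mostly wording, and medical history is already collected at screening (Table 5-1). Who may enrol does not change. The real price is size: total accrual is capped at 51, so the previously treated set may fall short of 25. Filling 25 would take about 34 Arm A patients if a quarter were untreated (25/0.75) and 50 if half were (25/0.50). Within the cap, the result will be less precise or the set will fill more slowly. The fix also leaves variation among previously treated patients, such as the 17% group, to be handled by the sensitivity range.
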